Lower extremities surgical intervention such as minor amputations (e.g. toe amputation) and reconstructive foot surgery (e.g. surgical offloading to fix chronic deformities) have become an important component of limb salvage effort to prevent major amputations (i.e. above ankle) and preserve maximum function in patients with diabetes and loss of protective sensation. Surgical wounds post lower extremities surgical interventions are mainly closed surgically. However, surgical wound complications such as infection, dehiscence, necrotic tissue, surgical revision, and poor cosmesis are unfortunately highly prevalent in patients undergoing lower extremities surgical interventions. In most cases surgical wounds are managed with a simple island dressing, orthopaedic wool padding and a light retention bandage. It could be argued that such low cost, traditional dressings are adequate for most surgical wounds. However, amputees with poor tissue integrity often require modern wound care products that offer additional benefits, in particular among those with vascular and poor tissue oxygenation problem. Poor tissue oxygenation and poor skin perfusion could lead to surgical wound complications such as wound inflection, tissue necrosis, phantom pain, trauma and untimely surgical revision as well as major amputation.

In particular, the presence of non-viable, necrotic tissue (estimated to occur in 15-25% of cases) is significant as it can be responsible for delaying healing, prolonging the inflammatory response, mechanically obstructing contraction and impeding re-epithelialisation. It also provides a focus for wound infection and surgical revision.

The problem associated with necrotic tissue is not limited to lower extremities and could be seen in other surgical closures leading to excessive scar formation. Many of these scars can be problematic, being aesthetically unpleasant and causing discomfort. Blood supply is a significant factor in wound healing, and area of the skin with rich supply of vasculature is known to heal with finer scars. Several studies have demonstrated that mild hypoxia (lack of transcutaneous oxygen) is present in early scars, moderate hypoxia in proliferative scars, and severe hypoxia in regressive scars. Oxygen levels then

return to normal in mature scars, which is consistent along with the dynamic change in microvessel density. Therefore level of transcutaneous oxygen could be a determinant factor in formation of excessive scar formation.

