Dressing materials are known to influence postoperative surgical wound healing and scar formation. A particular dressing that could promote wound hydration is key to ensure quick epithelialization and decrease excessive scar formation. The current standard of care in wound healing is to promote a moist wound environment by regular changing dressing and hydrate wound when needed. Some new advanced dressing and products have been also suggested with promising results in reducing excessive scar formation such as the use of silicone sheeting, hydrogel wound dressing, etc. However, level-1 evidence studies for effectiveness of such interventions are still lacking. Using advanced dressing enabling effective oxygen delivery to the wound bed could promote tissue hydration, which in turn could accelerate epithelialization and reducing the likelihood of formation of necrotic tissue and excessive scars.

In this study, we hypothesis that using novel dressing allows delivery tissue oxygenation via OxyGeni Oxygen Delivery System will reduce the likelihood of necrotic tissue as well as severe incisional scar post-surgical closure by improving transcutaneous oxygen levels during wound healing process. OxyGeni Oxygen delivery system is a novel wound healing therapy that promises to enhance tissue hydration, which in turn may lead to quick epithelialization essential to reduce the likelihood of formation of necrotic tissue and excessive scars. We will examine the validity of this hypothesis using a pilot randomized controlled trial using a convenient sample of 60 people (30 subjects per arm) with surgical wound closure.

Section D: Purpose and Objectives

We are proposing a clinical study at Baylor College of Medicine, to test the efficacy of the novel OxyGeni Oxygen delivery system for use in caring for patients with surgically closed wounds. We will assess the benefits of this novel therapy on successful closure, vascular parameters and quality of life. The study device OxyGeni is a Class II medical device which has US Food and Drug Administration (FDA) 510(k) clearance, CE-Mark approval and a Health Canada license for the treatment of wounds.

Here are the aims and hypotheses for this study:

Aim1: To assess effectiveness of OxyGeni oxygen delivery system in reducing the likelihood of wound complication postsurgical closure.

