Will pregnant women and/or fetuses (as described in 45 CFR 46 Subpart B) be enrolled in the research? No

E4. Neonates

Will neonates of uncertain viability or nonviable neonates (as described in 45 CFR 46 Subpart B) be enrolled in the research?

E5. Children

Will children be enrolled in the research?

Section F: Design/Procedure

F1. Design

Select one category that most adequately describes your research:

c) Pilot

Discuss the research design including but not limited to such issues as: probability of group assignment, potential for subject to be randomized to placebo group, use of control subjects, etc.

This study will be a 4 weeks prospective (or up to wound healing or surgical revision, whichever came first), experimental study with N=60 consecutive patients, who are undergoing surgical closure.

Subjects will be randomized to either control or intervention group. The intervention group will receive the OxyGeni device and place the oxygen delivery within SOC dressing. The control group will receive standard of care wound dressing.

All patients will have baseline assessment including visual, dermal, neuropathy (Vibration Perception Threshold) and vascular assessment (ABI and Skin Perfusion Pressure). Then, the status of wound closure and presence of wound complication will be monitored every week. Each subjects will need up to 5 visits including baseline assessment, and weekly assessment up to 4 weeks or full wound healing or surgical revision, whichever came first, and an additional follow-up visit at a minimum 6 months after the surgery. At each visit, patients will be provided standard of care treatment including physical assessment, debridement and offloading. Table 1 in attachments' section summarizes the key measurement at each study visit.

Please note that no screening activities will take place prior to the patient signing a consent form.

Inclusion Criteria:

18-85 years of age. Ability to provide informed consent. Presence of a wound due to surgical intervention and closure. Subject or responsible caregiver is willing and able to maintain the required offloading (as applicable for the location of the wound) and applicable dressing changes

Exclusion Criteria:

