Charcot Arthropathy Bilateral AK/BK amputation Active Drug/alcohol abuse (or history of drug/alcohol abuse in last 1 month) Dementia or impaired cognitive function Subjects with osteomyelitis or extreme gangrene. Excessive lymphedema Presence of active infection Subject has a history of or any intercurrent illnesses or conditions that would compromise the safety of the subject according to judgement of a qualified wound specialist.

F2. Procedure

Please note that subjects will be consented before performing any study related measurements. This study will not bring any direct costs to the subject. The subject's medical insurance will be billed for all standard of care procedures.

Subjects who are randomized in the intervention group will receive the OxyGeni therapy into their SOC dressing. Those subjects allocated to the control group will only receive Standard of Care treatment. We will be reviewing the billing records for our patients to explore costs of both groups.

We may visit the patient's home for an appointment that doesn't require the physician present or to fix any issues with the device.

There will be a follow up phone call up to three months after the last visit. Additionally, there may be an optional six month follow-up that can be conducted remotely (via a video or phone call) or in-person. During the virtual six month follow-up the patient will be asked to answer questionnaires electronically via REDCAP. This will also involve uploading a photo of the neck area to allow for virtual assessment of scarring/wound healing. Finally, the subject will be asked to upload a video of them performing 20 seconds of elbow flexion-extension to allow for virtual frailty assessment. Should the subject be available for an in-person visit, questionnaires will be conducted in clinic. Upper-extremity frailty test will also be conducted in the clinic per description listed below. Digital images of the neck area and images using the Kent camera will be taken to assess scarring and tissue perfusion.

Study Tasks:

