This is a pilot study. We plan to recruit a convenient sample of 60subjects (30 subjects per group), which we anticipate to be sufficient to observe a trend between groups to examine proof of concept of EO2 OxyGeni oxygen to reduce the likelihood of wound complication post-surgical wound closure. Based on our initial prevalence chart review, we anticipate that 20-30% of patients in the control group will have failure in wound closure (e.g. necrosis, tissue necrosis and its volume, infection, surgical revision). We anticipate to reduce the incident of wound complication to less than 5%. Using a chi-square test and assuming an alpha level of 5%, and ratio risk reduction of 25%, we anticipate to have statistical power of 95% using a 30 sample per group.

Based on this pilot study, we will calculate power and will design a clinical trial accordingly.

G2. Data Analysis

Provide a description of your plan for data analysis. State the types of comparisons you plan (e.g. comparison of means, comparison of proportions, regressions, analysis of variance). Which is the PRIMARY comparison/analysis? How will the analyses proposed relate to the primary purposes of your study?

The primary outcome of this study is the percentage of wound complication incidents post surgical interventions. We will use chi-square to estimate whether the number of wound complication incidents is less in the intervention group compared to the control group. The secondary outcomes of this study are: improvement in skin perfusion and reduction in perceived pain, anxiety, and stress. We will use general linear model (GLM) univariate analysis (UNIANOVA) to examine significant difference between groups for the secondary parameters of interest. Results will be adjusted by demographic information (age, gender, BMI) and clinical information (size of initial wound, A1C level, baseline skin perfusion).

Section H: Potential Risks/Discomforts

H1. Potential Risks/Discomforts

Describe and assess any potential risks/discomforts; (physical, psychological, social, legal, or other) and assess the likelihood and seriousness of such risks:

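### Wounds at different body sites appear to be pooled with no stratification or adjustment by site, so a chance imbalance could bias the primary estimate in either direction

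*Combined protocol and SAP*

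**What the plan says.** **Population.** The inclusion criterion in F1 is "Presence of a wound due to surgical intervention and closure", with no anatomical limit. F1 describes an "experimental study with N=60 consecutive patients, who are undergoing surgical closure", and the background section describes a "pilot randomized controlled trial using a convenient sample of 60 people (30 subjects per arm) with surgical wound closure". No quota by wound site is given.

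**Leg and foot content.** The background section says that "surgical wound complications such as infection, dehiscence, necrotic tissue, surgical revision, and poor cosmesis are unfortunately highly prevalent in patients undergoing lower extremities surgical interventions". Hypothesis H1 in Section D counts amputation as a complication. F2 measures vibration perception at the toe, heel and fifth metatarsal head, measures skin perfusion pressure and ankle-brachial index with ankle cuffs, and grades the foot by WIfI. The risk section describes tubing run along the legs.

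**Content on other sites.** The background section adds that necrosis also occurs after other surgical closures. F1 asks for offloading only where the wound's location calls for it. F2 describes the remote six-month follow-up as "uploading a photo of the neck area to allow for virtual assessment of scarring/wound healing", and the in-person version also images the neck.

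**Allocation.** The statement in F1 is "Subjects will be randomized to either control or intervention group". It does not say whether allocation is simple, blocked or stratified.

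**Analysis.** For the primary outcome, G2 says: "We will use chi-square to estimate whether the number of wound complication incidents is less in the intervention group compared to the control group". The adjustment list (age, gender, BMI, initial wound size, A1C, baseline skin perfusion) follows the model for the secondary outcomes and does not include site.

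**Expected rates.** G1 gives one figure for all sites: "Based on our initial prevalence chart review, we anticipate that 20-30% of patients in the control group will have failure in wound closure". It expects less than 5% in the intervention arm.

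**The concern.** On the protocol's own reasoning, blood supply drives healing and well-vascularised skin heals better. A leg or foot incision and a neck incision would then carry different complication risks, and amputation cannot be an outcome of a neck incision. If both are enrolled, site is a plausible strong predictor of the primary outcome.

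Nothing in the plan controls for it. Allocation is not stated to be stratified and the primary test has no covariates. Baseline skin perfusion is no substitute even where adjustment is planned, because F2 takes skin perfusion pressure at the ankle and describes it as a test of the feet. It says nothing about perfusion at a neck wound.

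Two things are at stake. With 30 per arm, part of the observed difference could reflect which arm received more leg wounds. Also, G1 says the later trial will be sized from this one, and a single pooled rate is hard to carry over unless the later trial recruits the same mix.

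**Working it through.** The plan gives no figure for case mix or for risk by site, so there is nothing on this point to reproduce. (G1's 95% power is a separate matter. At 5% in the intervention arm, the usual two-sided formula with 30 per group gives 42%, 59% and 73% for control rates of 20%, 25% and 30%.)

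**Inputs from the documents.** 60 subjects, 30 per arm; control rate 20-30%; intervention rate below 5%. Taking 5%, the planned difference is 20 − 5 = 15 to 30 − 5 = 25 points.

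**Inputs assumed.** Leg share 30%, 50% or 70%. Risk on the leg 25% (20-30%) and elsewhere 3% (1-5%).

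**Step 1: how often the arms differ in leg share.** With fixed 30:30 allocation and *K* leg wounds among 60, the number in one arm is hypergeometric(60, *K*, 30). A gap of 6 leg wounds is 6/30 = 20 points.

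| Leg share | P(gap of 6 or more) | P(gap of 10 or more) |
|---|---|---|
| 30% (*K* = 18) | 15.8% | 1.0% |
| 50% (*K* = 30) | 19.6% | 1.9% |
| 70% (*K* = 42) | 15.8% | 1.0% |

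These count gaps in both directions; half of them load the leg wounds onto control. Under simple randomisation, simulation puts a gap of 20 points or more at 10% (share 30% or 70%) to 16% (share 50%). The result does not depend much on which unstratified method is used.

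**Step 2: what a gap does when there is no treatment effect.** Shift = (gap / 30) × (leg risk − other risk).

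- Suppose control has 18 leg and 12 other wounds, and intervention has 12 leg and 18 other. Expected rates are (18 × 25% + 12 × 3%)/30 = 16.2% and (12 × 25% + 18 × 3%)/30 = 11.8%. The difference is 4.4 points. Within each site it is zero.
- Over the assumed risks, a gap of 6 gives 6/30 × (20 − 5) = 3.0 to 6/30 × (30 − 1) = 5.8 points.
- A gap of 10 gives 10/30 × 22 = 7.3 points.

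**Step 3: effect on the test.** The unadjusted chi-square was simulated with no treatment effect (400,000 trials per scenario; leg versus other risk of 30% v 5%, 45% v 5% and 30% v 10%; leg share 30%, 50% and 70%).

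- Averaged over all randomisations, two-sided type I error is 5.0-5.3% (simple) and 4.7-5.7% (fixed 30:30).
- Given that control has at least 20 points more leg wounds, the mean spurious benefit is about 5-10 points. A significant result favouring the device then occurs in 6-14% of trials, against a nominal 2.5%.
- With equal risk at both sites (25% v 25%), that figure stays at about 2.5%.
- With allocation stratified by site the gap is zero, but the plain chi-square becomes conservative (2.6-4.5%). The analysis should therefore be stratified too.

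**Step 4: the pooled control rate.** At 25%, 3% and half on the leg it is 0.5 × 25% + 0.5 × 3% = 14%. The extremes for a leg share of 25-75% are 0.25 × 20% + 0.75 × 1% = 5.8% and 0.75 × 30% + 0.25 × 5% = 23.7%.

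**The case against.** **The mix is inferred.** The neck text in F2 is written as if for every six-month participant, other descriptions of that visit mention only the scar, and the ankle and foot tests read as if every subject had a leg wound. No statement says that both are enrolled. This stands: the contradiction over the study population has to be settled first, and if one site dominates, the imbalance problem largely disappears.

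**The risk contrast is assumed.** G1 applies 20-30% to the whole control group and does not say that the chart review covered legs only. This also stands, but it need not shrink the problem. If 25% is the pooled rate, with half the wounds on the leg and 5% risk elsewhere, the leg risk is 45% and a 20-point gap shifts the difference by 6/30 × 40 = 8 points. If the sites have equal risk, the shift is zero.

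**The shift is modest.** At a 14% rate the standard error of the difference is √(2 × 0.14 × 0.86/30) = 9.0 points, so 4.4 points is about half a standard error. This is correct and limits how heavily the point should weigh.

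**This is an exploratory pilot, perhaps already under way.** The reconsent plan for the optional visit suggests that some subjects are already enrolled. That limits what a change in allocation can do, but not what a stratified analysis can do.

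**Stronger readings to avoid.** A reader might infer that simple randomisation is planned; the method is not stated. A reader might infer that the primary test has an inflated false-positive rate or is biased towards the device. Overall type I error is essentially kept, and an imbalance is as likely to hide an effect as to mimic one. A reader might also infer that the pilot cannot yield a usable rate. Rates can be tabulated by site whatever the allocation, and a pooled rate serves a later trial with the same mix.

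**Conclusion.** The point holds as a matter of conditional bias and interpretability. Eligibility has no anatomical limit, leg and neck content sit side by side unreconciled, no stratification is stated, and the primary comparison takes no account of site. The chance of a gap of 20 points or more in leg share is about 16-20% under unstratified 30:30 allocation, for leg shares of 30% to 70%. At assumed risks of 25% and 3% that gap moves the estimate by about 4.4 points in either direction, against a planned 15 to 25. The leg share and the site-specific risks are assumptions, and so is the enrolment of more than one site. The change is worth making because it is cheap and uses a fact known at baseline.

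**What to change.** 1. Reconcile the background section and F1 with the neck-specific text in F2, and state which wound sites are eligible.
2. State the randomisation method in F1. If more than one site is eligible, stratify the remaining allocation by lower extremity versus other, in permuted blocks.
3. In G2, make the primary comparison site-stratified (Mantel-Haenszel risk difference or Cochran-Mantel-Haenszel test) for all subjects, including those already randomised.
4. Report complication rates by site and arm, for use in sizing the later trial.

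**Cost.** A revised randomisation list and a few lines of text; no extra subjects, visits or procedures. The non-leg stratum may add little information: 30 such subjects at 3% yield 30 × 0.03 = 0.9 expected events. The gain in power is small.

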Pain Intensity Assessment (VAS): The subject will be provided with a numeric pain scale where he/she will report pain intensity. Research staff will document subject's pain level. (Measurements will be done at every visit)

WIFI wound classification (Wound, Ischemia, and foot infection): Podiatric (foot) physician will evaluate the health and wellness of the subject's feet in compliance of standard of care. (Will be done on screening/baseline visit and visit 4)

Screening/Baseline Visit *duration of visit 90 minutes This visit research staff will perform as described above: Medical History, Questionnaires (Pain, Social Factors, and Quality of Life, Sleep Quality, Cognitive Assessment, Frailty), Upper Extremity Test, Peripheral Neuropathy, Heart Rate Monitoring, Vascular Assessment, Wound Assessment, Wound Monitoring, Wifi Wound Classification, Dressing Change and Device Education.

Visit 1, One Week Later *duration 50 minutes This visit research staff will perform as described above: Pain Questionnaire, Heart Rate Monitoring, Adverse Event Reporting, Wound Assessment, Dressing Change and Device Education.

Visit 2, Two Weeks Later *duration of visit 80 minutes This visit research staff will perform as described above: Pain Questionnaire, Vascular Assessments, Heart Rate Monitoring, Adverse Event Reporting, Wound Monitoring, Wound Assessment, Dressing Change and Device Education.

Visit 3, Three Weeks Later *duration 60 minutes This visit research staff will perform as described above: Pain Questionnaire, Heart Rate Monitoring, Adverse Event Reporting, Wound Assessment, Dressing Change and Device Education.

Visit 4, Four Weeks Later *duration of visit 80 minutes This visit research staff will perform as described above: Questionnaires (Quality of Life, Acceptability, Pain, Frailty, Sleep Quality), Vascular Assessments, Heart Rate Monitoring, Adverse Event Reporting, Wound Monitoring, Wound Assessment, Dressing Change.

Visit 5, at a minimum of 6 months after surgery. This visit research staff will perform the SCAR assessment scale, POSAS,

and PASS questionnaires and take a digital picture of the scar. If the patient is unable to attend, the visit can be done remotely.

Section G: Sample Size/Data Analysis

G1. Sample Size

How many subjects (or specimens, or charts) will be used in this study?

Local: 60 Worldwide: 60

Please indicate why you chose the sample size proposed:

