As any new investigational device, there are some risks, which are anticipated to be minimal in this study. Some of potential risks could be: * Skin related discomfort, erythema (redness), skin rash, dryness and itching. * Skin allergic reaction to dressing adhesive. * Tenderness/minor ache around the dressing application area * Heat sensation and/or perspiration with wearing dressing * Some impairment of mobility due to dressing unit

Some of the study devices (OxyGeni LegSys, SensiLase) and technology are completely non-invasive, safe, non-toxic and non-ionizing. The potential risks are minimal. However, like any battery powered systems, there is a minimum risk of sensor malfunctioning. In addition, the study devices are not waterproof, and although they use a low powered battery (similar to a cell-phone battery), in order to avoid any risk of shock the monitor should not be submerged or saturated with fluids during operations or cleaning.

When wearing the study devices, there is a small risk of tripping. The dressing will be connected to the OxyGeni device through a thin tube that will be placed comfortably along the subject's legs underneath their clothing. We will instruct the subject to place the tube correctly to minimize any risk of tripping.

There is a minimal risk of interference from Zephyr Bioharness in the functionality of pacemaker/ICD devices. Therefore, to avoid any adverse events, it is recommend by the American Heart Associates to avoid the use of this wearable device on subjects with a pacemaker/IDC. There are no hazards or adverse events reported regarding Zephyr Bioharness.

Subjects must be willing to charge device battery daily. Otherwise they will not receive benefit from treatment.

The assessments described above are expected to be minimal risk and probability and magnitude of harm or discomfort anticipated in the research are not greater in and of themselves than those ordinarily encountered in daily life or during the performance of routine physical or psychological examinations or tests.

A vibration perception device will be used to monitor progress and diagnose severity of DPN in lower extremities. The vibration range will be from 0-25 Volts. Participants may feel slight discomfort from the vibration. This device is compliant with medical electrical device safety according to IEC 601-1.

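### The optional 6-month follow-up is told to image the neck, while eligibility admits wounds at any site and other sections refer to the wound or the scar

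*Combined protocol and SAP*

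**What the plan says.** F2 (Procedure) describes the late follow-up in these terms: "there may be an optional six month follow-up that can be conducted remotely (via a video or phone call) or in-person". For the remote form it adds: "This will also involve uploading a photo of the neck area to allow for virtual assessment of scarring/wound healing". For the in-person form: "Digital images of the neck area and images using the Kent camera will be taken to assess scarring and tissue perfusion". Neither sentence is conditional on wound site, and the neck is mentioned nowhere else in the document.

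Other sections point elsewhere:

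- **Eligibility (F1).** The wound criterion is "Presence of a wound due to surgical intervention and closure", with no anatomical limit. A further criterion expects the site to vary: "required offloading (as applicable for the location of the wound".
- **Background.** The rationale starts from toe amputation and reconstructive foot surgery, then widens: "The problem associated with necrotic tissue is not limited to lower extremities and could be seen in other surgical closures". The neck is not named.
- **Device set-up (H1).** The dressing is connected by a "thin tube that will be placed comfortably along the subject's legs underneath their clothing".
- **Visit 5 entry (end of F2).** Staff are to administer the scar scales "and PASS questionnaires and take a digital picture of the scar", with no site stated. The entry then allows the visit to be remote.
- **Study Tasks (F2).** Wound photographs and tissue-oxygen images are called for at every visit, and a Visit 5 photograph accompanies the SCAR scale. None of these is tied to the neck.

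**The concern.** Imaging is useful at 6 months only if it shows the incision that was treated. If the neck instruction is followed for a patient with a foot or leg closure, the picture shows skin that was never operated on.

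Two items in Section D depend on this visit. H5 is a practitioner-rated SCAR outcome, and SCAR is scheduled only at Visit 5, so no earlier rating can stand in for a lost one. The list of parameters of interest also includes perfusion at 6 months compared with baseline and with control. That comparison needs the same site imaged at both times.

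The remote visit is the weaker case. In clinic, staff can see the scar and correct for the wording. A patient at home who is asked for a neck photograph may simply send one, and the error may surface only when someone tries to rate it.

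**Working it through.** The plan gives no figure on this point, so the check sets the sections side by side.

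| Place | What is imaged or assumed | Tied to the neck? |
|---|---|---|
| F2, remote 6-month follow-up | Uploaded photo, for scarring and healing | Yes, unconditionally |
| F2, in-person 6-month follow-up | Digital images, plus Kent camera images, for scarring and perfusion | Digital images yes; Kent images unclear |
| F1, inclusion criteria | Any surgically closed wound | No |
| F2, Wound Assessment | Photo of the wound, every visit | No |
| F2, Vascular Assessment | Tissue-oxygen images every visit; ABI and skin perfusion pressure by ankle cuff | No |
| F2, SCAR task and Visit 5 entry | Photograph of the scar | No |
| H1, device description | Tube along the legs | No; assumes a leg route |

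**Step 1: do the sections agree?** No. For a patient with a neck closure, all the imaging instructions can be met with one picture. For any other patient, the two F2 follow-up sentences name one site and the Visit 5 entry names another.

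**Step 2: does another passage settle it for remote visits?** Not fully. The Visit 5 entry says to photograph the scar and that the visit can be remote. But only the F2 follow-up paragraph says what a remote patient must upload, and it says the neck.

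**Step 3: is there another view of the scar?** It depends on the mode. F2 allows a video or a phone call. A video call could show the scar live; a phone call could not.

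**Step 4: is perfusion affected?** The remote photo serves scarring and healing only. In person, the Kent images form a separate item in the sentence, which can be read as confining them to the neck or not. The 6-month perfusion comparison is therefore ambiguous as to site.

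**Step 5: how many subjects?** Let *a* be the share of the 60 who attend Visit 5, *s* the share of attendees whose wound is not on the neck, and *r* the share of those seen remotely.

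- Non-neck attendees, in either mode: 60 × *a* × *s*
- Of these, seen remotely: 60 × *a* × *s* × *r*

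The documents give none of *a*, *s* or *r*. Each lies between 0 and 1, so both counts can be anything from 0 to 60. That range carries no information, and no single value can be defended from the text.

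**The case against.** The strongest reply is that the intent is plain. The Visit 5 entry says to photograph the scar, the SCAR task pairs a photograph with the scar's appearance, wound photographs are called for at every visit, and even the neck sentence gives its purpose as assessing scarring and healing. Sensible staff would image the scar wherever it is. This stands as far as it goes: the text is a contradiction, not an unambiguous plan to image only the neck. It does not remove the problem for a remote patient following a literal upload request.

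A reader might infer more than the documents support:

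- **That every subject is affected.** The visit is optional in F2, and J2 requires separate reconsent for it.
- **That remote non-neck patients would have no usable scar data.** A video call could show the scar, and nothing says the SCAR rating must rest on the uploaded photo alone.
- **That 6-month perfusion is lost.** The Kent images are not clearly confined to the neck, and the every-visit imaging instruction has no site limit.
- **That about a quarter of the trial is exposed.** Taking half the wounds as non-neck and half of those patients as remote gives 60 × 0.5 × 0.5 = 15, or 25%. Both halves are arbitrary, and the figure assumes that all 60 attend an optional visit.
- **That nearly all wounds are on the leg or foot.** The background leads with the lower limb but explicitly extends to other closures.

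It is also fair to say that the stakes are limited. G2 makes wound complications the primary outcome and does not list scar appearance among the secondary outcomes. H2 measures perfusion at baseline, 2 and 4 weeks; the 6-month time point appears only in the parameter list of a study that calls itself exploratory. Finally, F1 refers to an attached table of measurements by visit that is not among the documents reviewed and might clarify the site.

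**Conclusion.** The point holds as an internal contradiction. For the optional 6-month follow-up, F2 fixes the remote photo and the in-person digital images to the neck without any wound-site condition. F1 admits any site, H1 assumes a leg route for the tube, and the tasks and visit entry refer to the wound or the scar. Followed literally, the F2 image would not show the treated incision of a non-neck patient.

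The consequence is most serious for remote visits, especially by phone, because SCAR is collected only then. In-person digital images are affected too; the Kent images are ambiguous as to site. What is exposed is H5 and the 6-month perfusion comparison, both exploratory. The primary outcome is not touched. The number of subjects cannot be derived from the documents.

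The conclusion assumes that at least some Visit 5 attendees have wounds away from the neck, which the eligibility criteria allow but do not guarantee.

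**What to change.** In both F2 follow-up sentences, replace the reference to the neck with the index surgical incision recorded at baseline, in line with the Visit 5 entry. State that the Kent camera images are of that same site. Use the same wording in any upload instruction sent to remote patients, so that each is asked for a photograph of their own wound site.

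If a neck-closure cohort is what is intended for Visit 5, say so explicitly and limit H5 and the 6-month perfusion comparison to that group.

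The first option costs a wording change in two sentences and any matching upload text, and adds no visit or procedure. The second also needs only text, but narrows the group to which the 6-month results apply.
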